## LIST OF ABBREVIATIONS AND DEFINITIONS OF TERMS

21CFR	United States Code of Federal Regulations, Title 21
ADA	anti-drug antibody
ADR	adverse drug reaction
AE	adverse event
AESI	adverse event of special interest
ALB	albumin
ALK-P	alkaline phosphatase
ALL	acute lymphoblastic leukemia
ALT	alanine aminotransferase
AML	acute myeloid leukemia
ANC	absolute neutrophil count
APTT	activated partial thromboplastin time
AST	aspartate aminotransferase
BID	twice daily
BP	blood pressure
bpm	beats per minute
BUN	blood urea nitrogen
Ca	calcium
CAR	chimeric antigen receptor
CBC	complete blood count
CDR	complementary-determining region
CFR	Code of Federal Regulations
CI	confidence interval
CK	creatine kinase
Cl	chloride
C max	maximum concentration
CNS	central nervous system
COVID-19	coronavirus disease-2019
CR	complete remission (mCR, CRc, or CRm)
CR1	initial CR
CRc	cytogenetic complete remission
CRh	complete remission with partial hematologic recovery
CRi	complete remission with incomplete blood cell recovery
CRm	molecular complete remission
CRn	CR with incomplete neutrophil recovery
CRp	CR with incomplete platelet recovery
CRS	cytokine release syndrome
CTCAE	common terminology criteria for adverse events
DLCO	carbon monoxide diffusion capacity in the lung

DLT	dose-limiting toxicity
DP	drug product
DSM	Data Safety Monitor
EBV	Epstein-Barr virus
EC	effective concentration
$EC_{10}$	concentration at 10% of the maximum effect
ECG	electrocardiogram
ECOG	Eastern Cooperative Oncology Group
eCRF	electronic case report form
EFS	event-free survival
ELISA	enzyme-linked immunosorbent assay
EMD	extramedullary disease
EOTV	End of Treatment Visit
ER	early relapse
E:T	effector to target ratio
FDA	Food and Drug Administration
FEV1	forced expiratory volume in 1 second
FIH	first-in-human
FISH	fluorescence in situ hybridization
GCP	Good Clinical Practice
GLP	Good Laboratory Practice
GM-CSF	granulocyte macrophage-colony-stimulating factor
GvHD	graft versus host disease
Hct	hematocrit
HSCT	hematopoietic stem cell transplantation
Hgb	hemoglobin
HIPAA	United States Health Insurance Portability and Accountability Act
HIV	human immunodeficiency virus
IB	Investigator's Brochure
ICH	International Conference on Harmonisation
IDMC	Independent Data Monitoring Committee
IFN-γ	interferon gamma
IHC	immunohistochemistry
IL-3Ra	interleukin-3 receptor alpha chain
IND	Investigational New Drug
IPSS	International Prognostic Scoring System
IRB/IEC	Institutional Review Board/Independent Ethics Committee
IRE	immediately reportable event
IRR	infusion-related reaction
IUD	intrauterine device
IV	intravenous

IWG	International Working Group
К	potassium
LSC	leukemic stem cells
LVEF	left ventricular ejection fraction
mAb	monoclonal antibody
MABEL	minimum anticipated biological effect level
mCR	morphologic CR
MDS	myelodysplastic syndrome
MLFS	morphologic leukemia-free state
MRD	minimal residual disease
MTD	maximum tolerated dose
MTDS	maximum tolerated dose and schedule
MUGA	multiple-gated acquisition scan
Na	sodium
NCI	National Cancer Institute
NK	natural killer
NOAEL	no observed adverse effect level
NOD/SCID	non-obese diabetic/severe combined immunodeficient
OB	other benefit
OCRR	overall complete response rate
OS	overall survival
PBMC	peripheral blood mononuclear cell
PD	progressive disease
pDC	plasmacytoid dendritic cell
PFT	pulmonary function test
PIF	primary induction failure
РК	pharmacokinetics
РО	by mouth
PR	partial remission
PS	performance status
РТ	prothrombin time, preferred term
qw	once weekly
SAE	serious adverse event
SARS-CoV-2	severe acute respiratory syndrome coronavirus 2
SC	subcutaneous
SD	stable disease
TCR	T-cell receptor
TEAE	treatment-emergent adverse event
TLS	tumor lysis syndrome
ULN	upper limit of normal
US	United States

USPUnited States PharmacopeiaWBCwhite blood cell (count)WHOWorld Health Organization

## 1 SYNOPSIS

Sponsor: MacroGenics, Inc.	IND Number: 116832
	EudraCT Number: 2015-003813-11

Name of Finished Product: Flotetuzumab, MGD006 (CD123 x CD3 DART protein)

**Study Title:** A Phase 1/2, First-in-Human, Dose Escalation Study of MGD006, a CD123 x CD3 Dual Affinity Re-Targeting (DART) Bi-Specific Antibody-Based Molecule, in Patients with Relapsed or Refractory Acute Myeloid Leukemia or Intermediate-2/High Risk Myelodysplastic Syndrome

Study Number: CP-MGD006-01

#### **Investigator(s)/Centers:**

The study will be carried out at approximately 50 institutions globally, preferably with experience in the conduct of studies in patients with acute myeloid leukemia (AML) or myelodysplastic syndrome (MDS).

Study Phase: 1/2

#### **Primary Objective:**

To assess the anti-neoplastic activity of flotetuzumab in patients with PIF/ER AML, as determined by the proportion of patients who achieve CR/CRh.

#### **Secondary Objectives:**

- Assessment of CR rate, CRh rate, overall complete response rate (OCRR; CR, CRh, CRi [CRn, CRp], or MLFS), objective response rate (CR, CRh, CRi [CRn, CRp], MLFS, or PR), time to response and duration of response (DOR).
- To measure early mortality rates, overall survival (OS) and event-free survival (EFS).
- To determine the rate of eligible patients, per institution criteria, that transition to successful stem cell transplant after achieving overall complete response (CR, CRh, CRi [CRn, CRp], or MLFS).
- To assess rate of conversion to and maintenance of transfusion independence.
- To evaluate duration of initial hospitalization for flotetuzumab administration.
- To evaluate incidence and duration of hospitalizations subsequent to initial discharge.
- To monitor the safety and tolerability of flotetuzumab.
- To characterize the PK and immunogenicity of flotetuzumab.
- To determine safety and efficacy of tocilizumab in the treatment of IRR/CRS.

Exploratory Objectives: Refer to Section 3.3 for complete list of exploratory objectives.

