The above design yields a 1-sided alpha of 0.005 for the efficacy boundary at the second interim analysis and an overall 1-sided alpha of 0.024 with approximately 80% power at the final analysis. The probability of early termination under H0 (futility) in the first two stages is 55%.

The primary efficacy endpoint for the AML expansion cohort is the CR/CRh rate, calculated as the proportion of patients in the efficacy population that has achieved a best response of CR (mCR, CRc, or CRm) or CRh at any point during treatment by investigator's assessment, according to IWG AML response criteria (**Appendix 3**). CR/CRh rate will be summarized for the total combined PIF/ER patients as the primary analysis, as well as for PIF and ER patients separately, and for PIF/ER patients in the response-evaluable population as a sensitivity analyses. A two-sided exact 95% confidence interval will be calculated around response rates.

For the second interim analysis of 100 patients, as well as for the final analysis of 170 patients, all treated patients will be followed for at least 6 months or until death from any cause, whichever occurs first, prior to data cutoff for the analysis. If the trial passes the prespecified efficacy boundary (25% observed CR/CRh rate) at the second interim analysis, a two-sided exact 95% confidence interval as described by Jennison and Turnbull (21) will

be produced to account for the bias in the conventional exact confidence interval for fixed sample test.

The key secondary efficacy endpoints include CR rate, CRh rate, duration of response, post-baseline transfusion independence rate, hematopoietic stem cell transplantation (HSCT) rate, and incidence and duration of hospitalization. Additional secondary efficacy endpoints include overall complete response rate, objective response rate, subgroup analyses of CR/CRh, CR, CRh and overall complete response rates, overall survival, event-free survival, time to response, mortality rate at 30, 60, 90, and 180 days, six-month and one-year survival. Counts, percentages, and two-sided exact 95% confidence intervals will be used to describe categorical secondary variables. Kaplan-Meier (KM) methods will be used to estimate time-to-event endpoints, unless otherwise specified. All secondary efficacy endpoints will be summarized in both efficacy and response evaluable population by PIF, ER, and total.

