#### General Administration Information:

**Flotetuzumab must not be administered as an IV push or bolus**. During the Cohort Expansion Phase, at least for the first 8 days of Cycle 1 (and after a minimum of 24 hours at the 500 ng/kg/day maximum dose), the drug will be administered in an inpatient hospital setting; but afterwards may be administered in an outpatient setting as described in **Section 4.1.1**. The type of pump used for administration of flotetuzumab may differ by country or region. It is important that at any point, THE INFUSION BAG CONTAINING FLOTETUZUMAB MUST NOT BE SHAKEN; excessive agitation may cause aggregate formation. Subsequent to Cycle 1 Day 8 (and after a minimum of 24 hours at the 500 ng/kg/day maximum dose), patients may, as appropriate (see **Section 6.3**), receive flotetuzumab as a continuous infusion in an outpatient setting using an ambulatory pump configuration. Specific instructions for dose preparation and administration in both the inpatient settings are provided in the Pharmacy Manual.

Sites must ensure patients who receive flotetuzumab in the outpatient setting will be provided instructions and trained appropriately and monitored for compliance and safety.

Flotetuzumab should not be admixed or diluted with other drugs. Any partially used vials or diluted dosing solutions should be discarded using appropriate drug disposal procedures.

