The overall complete response rate (BM blasts < 5%) will be the proportion of patients with AML achieving any CR, CRh, CRi, [CRn, CRp], or MLFS when such responses are documented at any point of any cycle of treatment. The objective response rate will be the proportion of patients with AML achieving CR, CRh, CRi, [CRn, CRp], MLFS, or PR when such responses are documented at any point of any cycle of treatment. To support the composite endpoint CR/CRh, the duration of initial hospitalization for flotetuzumab administration, the incidence and duration of subsequent hospitalizations, and transfusion independence rate, as well as rate of conversion to transfusion independence and rate of maintenance of transfusion independence, will be assessed. The timing of the AML response evaluation, i.e., the allowance for response at a time later than Day 25 from the start of treatment, differs from those modified from the IWG guidelines for AML (which are based on responses to cytotoxic chemotherapy) to allow sufficient time for an immune-mediated response to be observed. Patients who do not demonstrate an objective response at early evaluations, may be subsequently categorized as responders at later evaluations. Response duration will be calculated from the time of initial response to the time of relapse or death, whichever occurs first. Patients who complete the study while still in response will be

censored at their last disease assessment. Time to response will be calculated from the time of first dose of study drug to the time of initial response.

Event-free survival (EFS) will be calculated as the time from the first dose of study drug until date of relapse from CR, CRh, or CRi (CRn, CRp), or death from any cause, whichever occurs first.

Overall survival (OS) will be calculated as the time from the first dose of study drug until the occurrence of death from any cause. Mortality rates from any cause within 30, 60, 90, and 180 days from the first dose of study drug will be calculated. Six-month and one-year survival rates will be calculated.

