# 9.6.2.1 Key Secondary Efficacy Analyses

The key secondary efficacy endpoints include CR rate, CRh rate, duration of response, postbaseline transfusion independence rate, HSCT rate, and incidence and duration of hospitalization.

**Duration of response (DOR)** will be calculated from the time of initial documentation of response to the time of disease relapse or death due to any cause, whichever occurs first. Patients who are still in response at study completion without alternative therapies will be censored at the time of their last disease assessment. Duration of response will be calculated

for patients who achieve the first evidence of CR or CRh as primary analysis. A separate exploratory analysis will be conducted for patients who achieve the first evidence of overall complete response (CR, CRh, CRi [CRn, CRp], or MLFS).

**Post-baseline transfusion independence** is defined as no transfusion during any consecutive 56-day period on-study. Post-baseline transfusion independence will be summarized for RBC and platelet transfusion separately and in total. Transfusion dependence at baseline is defined as any red blood cell or platelet transfusions during the 28 days prior to the first dose of study drug. The rate of conversion from transfusion dependence to transfusion independence will be calculated. The rate of patients who are transfusion independent at baseline and remain independent during any 56-day post-baseline period will also be calculated.

**HSCT rate** is defined as rate of successful HSCT through study treatment. Patients who received other therapies (except for conditioning therapy) for AML after discontinuation of study drug and later undergo a subsequent HSCT will not be included. Number and percentage of patients with HSCT will be summarized.

**Incidence and Duration of Hospitalization,** summaries will be provided for the efficacy population, as well as independently for patients who achieved CR or CRh. Summaries will include duration of initial hospitalization as well as incidence, number and duration of subsequent hospitalizations following the initial discharge, number of days hospitalized, and the reasons for hospitalization.

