HSCT rate is defined as rate of successful HSCT through study treatment. Patients who received other therapies (except for conditioning therapy) for AML after discontinuation of study drug and later undergo a subsequent HSCT will not be included. Number and percentage of patients with HSCT will be summarized.

Incidence and Duration of Hospitalization, summaries will be provided for the efficacy population, as well as independently for patients who achieved CR or CRh. Summaries will include duration of initial hospitalization as well as incidence, number and duration of subsequent hospitalizations following the initial discharge, number of days hospitalized, and the reasons for hospitalization.

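### The hospitalization key secondary endpoint is summarized as raw stay lengths and raw counts, with no rule for death in hospital and no time-at-risk denominator

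*Protocol*

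**What the plan says.** The secondary objectives (Protocol Synopsis and 3.2; SAP 3.2) include "To evaluate duration of initial hospitalization for flotetuzumab administration", and a second one on the incidence and duration of later hospitalizations. Protocol 9.6.2.1 places the endpoint among the key secondary efficacy endpoints: "HSCT rate, and incidence and duration of hospitalization". SAP 11.2.1 describes the summary as "duration of initial hospitalization as well as incidence, number and duration of subsequent hospitalizations following the initial discharge, number of days hospitalized", plus reasons for hospitalization; Protocol 9.6.2.1 has the same content. On groups, SAP 11.2.1 states: "summaries will be provided for the efficacy population, as well as independently for patients who achieved CR or CRh".

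Protocol 7.10 gives the purpose: "To support the composite endpoint CR/CRh, the duration of initial hospitalization for flotetuzumab administration", listed with later hospitalizations and transfusion independence.

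The general rules do not fill the gap:
- SAP 7.1 summarizes continuous variables by mean, SD, median, minimum and maximum.
- SAP 11.2 uses Kaplan-Meier for time-to-event endpoints, but hospital stay has no event or censoring definition. Duration of response, OS and EFS each have one.
- SAP 7.2 on missing data does not address outcomes cut short by death.

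Three other provisions matter. Protocol 6.2.1.2 requires inpatient dosing "at least for the first 8 days of Cycle 1". Protocol 4.1.1 requires hospitalization for the first 24–48 hours when dosing restarts after an interruption of more than 24 hours. The follow-up data items in Protocol 8.3.2 do not list hospitalizations.

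**The concern.** A hospital stay can end in discharge or in death, and the raw length treats the two alike. A patient who dies during the first admission also cannot have a later one, because later stays are counted only after the initial discharge. That patient contributes a finished stay and zero readmissions. With inpatient dosing for at least eight days, a stay of under eight days from Cycle 1 Day 1 points to death or an early stop of treatment, yet it lowers the reported duration.

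Readmission counts and total hospital days also accumulate with time on treatment and with survival. CR/CRh patients must survive to a marrow assessment (Day 25 + 3 days in the response appendix) and may receive up to two consolidation cycles, so they have longer to accumulate admissions. Their separate summary is therefore not on the same footing as that of the whole efficacy population.

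What is at stake is interpretation. The figures are meant to support CR/CRh in a single-arm trial that the SAP calls pivotal, and as defined they mix burden of care with survival.

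**Working it through.** The documents give no target, sample size or expected value for this endpoint, so there is no stated figure to reproduce. The sizing at 40, 100 and 170 patients concerns CR/CRh only. The documents also give no stay lengths, death times in hospital or readmission rates, so what follows is illustration under stated assumptions.

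**1. Initial stay, constant death hazard.** Assume that a survivor's stay is 8 days (Protocol 6.2.1.2) plus an exponential time with mean 14 days. With 30-day mortality m, the death hazard is h = −ln(1−m)/30.
- Raw median of the earlier of discharge and death: t = (ln 2 + 8/14) / (h + 1/14).
- Live-discharge incidence: F(t) = e^(−8h) × (1/14)/(h + 1/14) × [1 − e^(−(h+1/14)(t−8))]; solve F(t) = 0.5.
- Share of stays under 8 days: 1 − e^(−8h).

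| m | h per day | Raw median, days | Half discharged alive by, days | Stay < 8 days |
|---|---|---|---|---|
| 10% | 0.00351 | 16.9 | 18.3 | 2.8% |
| 20% | 0.00744 | 16.0 | 19.2 | 5.8% |
| 30% | 0.01189 | 15.2 | 20.3 | 9.1% |

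Raw stay falls as mortality rises, while time to live discharge lengthens.

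**2. Initial stay, later inpatient deaths.** Keep the same discharge model, but let a fraction f remain inpatient and die uniformly over Days 15–35 (assumed).
- Raw median: solve (1−f) e^(−(t−8)/14) + f(35−t)/20 = 0.5.
- Half discharged alive: (1−f)[1 − e^(−(t−8)/14)] = 0.5.

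| f | Raw median, days | Half discharged alive by, days |
|---|---|---|
| 0 | 17.7 | 17.7 |
| 10% | 18.7 | 19.4 |
| 20% | 19.7 | 21.7 |
| 30% | 20.6 | 25.5 |

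Now the raw median rises. With deaths spread over Days 8–30 (second term f(30−t)/22) it is almost flat: 17.9, 18.0 and 18.2 days. The direction of the raw summary thus depends on when patients die. Time to live discharge lengthens with mortality in both tables.

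**3. Readmissions at one common rate.** Assume a 14-day first stay and counting to 28 days after last dose. That is the usual end of AE collection in Protocol 7.11.4, borrowed because no hospitalization window is stated. Days at risk:
- in-hospital death: 0
- one cycle: 28 + 28 − 14 = 42
- two cycles: 56 + 28 − 14 = 70
- CR/CRh in Cycle 1 plus two consolidation cycles: 84 + 28 − 14 = 98
- eight cycles, the maximum: 224 + 28 − 14 = 238

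At an assumed 0.5 readmissions per 30 days, expected counts are 0, 0.70, 1.17, 1.63 and 3.97. Rates of 0.25 or 1.0 halve or double them.

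**4. The comparison the plan presents: CR/CRh patients against the whole efficacy population.** Give every responder 98 days and every non-responder 42 or 70. The ratio of expected counts is then free of the rate.
- Response 23%: 98/(0.23×98 + 0.77×42) = 98/54.88 = 1.79; with 70 days, 98/76.44 = 1.28.
- Response 14.7%: 98/(0.147×98 + 0.853×42) = 98/50.23 = 1.95; with 70 days, 98/74.12 = 1.32.

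**5. Break-even.** The three-cycle responder shows more admissions only if the responder's rate exceeds 42/98 = 43% of a one-cycle non-responder's rate, or 70/98 = 71% of a two-cycle non-responder's.

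**The case against.** The strongest reply is that this is a descriptive summary in a single-arm trial, with no test attached. Mortality at 30, 60, 90 and 180 days and OS are reported on the same patients, so early deaths are visible. Reasons for hospitalization are collected, which should let admissions required on restarting treatment be identified. Inclusion criterion 5 asks for a life expectancy of at least four weeks, which argues against many deaths in the first week. Table shells and reporting conventions sit in a Statistical Programming Plan outside these documents.

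Much of this stands, and it limits the point. A reader might infer that the reported stay looks better the more patients die. The documents do not support that: only very early deaths shorten it, and step 2 shows the opposite with later deaths. A reader might infer that responders must look worst. That needs readmission rates the documents do not give, and step 5 shows how far a lower responder rate would reverse it. A direct contrast of responders with non-responders would look larger, but the plan does not present that comparison.

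The gap itself remains. Reporting mortality elsewhere does not change a stay length in which death counts as the end of the stay, and listing reasons does not supply a denominator. How to treat a competing event belongs in the SAP with the other endpoint definitions.

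**Conclusion.** The point holds as a weakness in how the endpoint is summarized. The raw duration mixes discharge with death, and its direction of error is unpredictable: in the illustrations the median moves by 1.7 days down or 1.9 days up as mortality goes from 10% to 30%. At equal monthly rates the CR/CRh summary is biased toward more admissions, by a factor of about 1.3 to 2.0 for a three-cycle responder. These sizes rest on the assumed stay distribution, death times and window. Whether responders would actually look worse is unknown.

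It would go too far to infer that the trial's error rate or its primary conclusion is affected, or that the hospitalization data are of no use. The endpoint is untested, and the same dates can be summarized soundly.

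**What to change.** Amend Protocol 9.6.2.1 and SAP 11.2.1 as follows.

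1. Report the initial stay from Cycle 1 Day 1 as cumulative incidence of discharge alive, with in-hospital death as the competing event. Show the number of in-hospital deaths beside it.
2. Among patients discharged alive, report later admissions and hospital days per patient-month at risk, for the efficacy population and for CR/CRh patients. State explicitly the window over which hospitalizations are collected. Use the recorded reasons to show separately the re-initiation admissions required by Protocol 4.1.1 and admissions for transplant.

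The cost is revised wording and a few extra tables. The figures may look less favourable than a raw median stay.

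Days alive and out of hospital could be added as an optional supplement over the collected window, but should not be the headline. It counts transplant admissions as lost days although successful HSCT is itself a key secondary endpoint. Carrying it to Day 180 would need hospitalization dates that the follow-up items in Protocol 8.3.2 do not list. The six-month minimum follow-up in Protocol 9.6.1 does not by itself guarantee those dates.
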